#### **4.2.5 Brain MRI: Safety**

MRI scans will be performed at Screening and Month 18 or in the event of early termination. The primary intent of the MRI assessments was to support eligibility for the trial and key secondary objectives of evaluating the effect of TTP488 on MRI brain volumetric measures.

Variables of analysis will include number (%) of subjects with:

- Presence of vasogenic edema as categorized as:
  - No vasogenic edema present;
  - Questionable presence of vasogenic edema;
  - Vasogenic edema present, mild severity;
  - Vasogenic edema, moderate severity,
  - Vasogenic edema present, severe severity.

- The status of vasogenic edema at Month 18 compared to baseline will be evaluated as the number (%) of subjects categorized as vasogenic edema either present or absent on prior MRI; if present, further categorized as:
  - Vasogenic edema present and unchanged in size,
  - Vasogenic edema present and increased in size,
  - Vasogenic edema present and decreased in size.

#### **4.3 Pharmacokinetics Variables**

Blood samples for TTP488 and metabolite (TTP2123, TTP1494, TTP2266) plasma concentrations will be collected prior to dosing at Months 3, 6, 12, 18 and 21 or at Early Termination. All participants with at least one dose of study medication will be included in the pharmacokinetic analysis. Variable of analysis will be plasma trough concentration at each time point.

#### **4.4 Pharmacodynamics Variables**

Blood samples for plasma biomarkers analysis will be collected prior to dosing on Baseline, Months 3, 6, 12, 18, 21 or at Early Termination.

All participants with at least one dose of study medication will be included in the pharmacodynamic analyses. For individual endpoints, participants must have at least 1 post-dose pharmacodynamic measurement for the given endpoint. For change from Baseline, participants must also have a Baseline value. Variables of analysis will be Plasma A $\beta$  (total, 1-40 and 1-42) concentration and change from baseline over time.

#### **4.5 Adverse Events of Special Interest**

Adverse events related to signs and symptoms of AD potentially pertain to efficacy as well as safety of the compound. Analysis of prior study data suggest the potential abatement of the signs and symptoms of AD that are associated with worsening of AD. Specifically, TEAEs classified by MedDRA into the SOC for psychiatric disorders (at the SOC level within the hierarchy of MedDRA) and specifically high level group terms (HLGTs) of anxiety disorders and symptoms (at the HLGT level within the hierarchy of MedDRA) will be variables of interest for comparison.

Standardized MedDRA queries (SMQs) will be used for dynamic analysis of any TEAE that emerges of potential interest.

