Three interim analyses were planned during the study. The first interim analysis was conducted 6 months after approximately 50% of participants had been randomized. This analysis was conducted for the purposes of safety and for informing internal development decisions. The second interim analysis was conducted 12 months after all participants were randomized to assess futility, as well as for safety and to inform internal development decisions. A third interim analysis to inform internal development decisions was to be conducted when all continuing participants completed the Month 18 visit.

The first pre-specified interim safety analysis revealed an increased frequency of AEs (concentration related and reversible upon discontinuation of treatment), in particular falls and confusion, in the 20 mg/day group relative to the 5 mg/day and

placebo groups. This was associated with a higher percentage of participants in the 20 mg/day group declining by ≥ 10 points on the ADAS-cog (relative to Baseline scores) at Months 3 and 6 (concentration related and stabilized/reversible upon discontinuation of treatment). These findings were not noted for the 5 mg/day group or the placebo group. On the recommendation of the Data and Safety Monitoring Board (IDMC), participants randomized to the 20-mg/day dose discontinued study drug, received a safety evaluation, and were asked to consent to continue to be followed for safety clinical and laboratory assessments.

Approximately 12 months after all participants were randomized, the second pre-specified interim analysis compared 5 mg/day and placebo for futility based on results of the completer population (i.e. those with available 18-month ADAS-cog data). Conditional power was computed based on assumed continuation of the observed trend.

While safety data raised no concerns, criterion for futility ($< 10\%$ conditional power to observe a significant difference between 5 mg/day and placebo at 18 months) was met and treatment was discontinued. The third interim analysis was not performed as the study was terminated due to futility. Attempts to replicate the futility analysis, using a data set representative of that which would have been used for the futility analysis (constructed from the final data set) have been unsuccessful with conditional probabilities consistently computed as $> 20\%$.

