Exploratory analysis of concentration-driven assessment of PK/PD effects included the quantile cuts described above and also iterative analysis focused on identification of a concentration range that was associated with optimal effectiveness for efficacy measures (primary and secondary measures). The iterative analysis included construction of groups with minimum trough concentrations ranging from 1 to 20 ng/ml. Within these groups, ranges were derived using optimization techniques to identify concentration groups that maximized efficacy. The results of the exploratory

PK/PD analysis concluded that the optimal trough concentration range was 8-15 ng/ml over the 18-month period.

Based on the considerations outlined above, a 5 mg/day dose was selected. Doses below 5 mg/day and between 5 mg/day and 20 mg/day were considered. Doses below 5 mg/day are expected to provide non-efficacious concentrations. Doses above 5 mg/day (ex: 10 mg/day) are not expected to provide significantly improved efficacy relative to the potential for achieving concentrations associated with acute, reversible cognitive worsening.

Preliminary evaluation of the effect of food on the pharmacokinetics of azeliragon has been performed from data collected in the TTP488-101 and TTP488-102 studies. Comparison of dose normalized pharmacokinetics for data obtained from Study TTP488-101 (single, ascending doses administered under fasting conditions; 5, 10, 20, 35, 50, and 65 mg) and the first administered dose, under fed conditions, from Study TTP488-102 (multiple dose administration; 15, 30, 60, and 30 mg in elderly subjects) demonstrate up to an approximate

30% decrease in C_{max} and AUC_{0-24} when administered in the fed state. This magnitude of difference in PK between fed and fasted state is not anticipated to be clinically meaningful for subjects dosed with 5 mg/d (anticipated concentration 8 to 15 ng/mL fasted; 10 to 20 ng/mL fed) as concentrations will be within the range associated with efficacy in TTP488-203 and well below those associated with the acute, reversible cognitive worsening in the 20 mg/d group (>47 ng/mL).

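### SAP 4.5 picks its special-interest events for expected benefit and does not pre-specify the Phase 2 harm signals: falls, confusion and early ADAS-cog decline of 10 or more points

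*SAP*

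**What the plan says.** **Special-interest events.** SAP 4.5 regards events tied to the signs and symptoms of AD as bearing on both efficacy and safety, and explains its choice thus: "Analysis of prior study data suggest the potential abatement of the signs and symptoms of AD that are associated with worsening of AD". It names the psychiatric disorders SOC as a whole and "specifically high level group terms (HLGTs) of anxiety disorders and symptoms". It closes with an open clause: "Standardized MedDRA queries (SMQs) will be used for dynamic analysis of any TEAE that emerges of potential interest". No query is named. SAP 5.4.1 handles these events in the same way as any other TEAE.

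**Phase 2 signal.** Protocol 1.1.3 says the first interim safety look at the earlier 18-month study found more adverse events, "in particular falls and confusion, in the 20 mg/day group". A higher percentage of that group was also "declining by ≥ 10 points on the ADAS-cog (relative to Baseline scores) at Months 3 and 6". Both findings are described as related to concentration. The events were reversible, and the cognitive decline stabilised or reversed, once treatment stopped. The 20 mg/day arm then came off study drug. The same section says neither finding was noted at 5 mg/day or on placebo. Protocol 1.1.4 expects concentrations at 5 mg/day to be "well below those associated with the acute, reversible cognitive worsening in the 20 mg/d group", which it places above 47 ng/mL.

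**Exposure-response.** Protocol 9.9 plans concentration-response work that includes safety data, and SAP 1.1 keeps an exposure-response objective that lists adverse events. SAP 5.5 provides for trough concentrations over the 18 months and no formal inference.

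**The concern.** A list of special-interest events normally starts from the harms already seen with the drug. Here the list starts from a hoped-for benefit, and the harms reported in the sponsor's own Phase 2 study are not on it. Those harms led to the 20 mg/day arm being stopped, and the protocol uses the cognitive worsening to argue against doses above 5 mg/day.

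The risk is to the final safety report. Related terms may be counted under separate preferred terms, so a modest excess of falls or confusion could be hard to see in general tables. No between-arm difference with an interval is planned for either. A group of patients with a sharp early cognitive drop could also be hidden within mean change, or within an 18-month time-to-worsening analysis in which ordinary progression accumulates.

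**Working it through.** The plan gives no figure to reproduce. The check compares the texts and then does two short calculations.

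**Step 1. Each Phase 2 signal against the SAP.**
- *Falls.* Not named in SAP 4.2 or 4.5, and no named category is stated to contain them. They would be counted by arm in the general TEAE tables by SOC and preferred term (SAP 4.2.1, 5.4.1).
- *Confusion.* Not named. The whole psychiatric SOC is included and may contain confusion terms, but the documents do not say where such terms code. A comparison at SOC level would not isolate them.
- *ADAS-cog increase of 10 or more points at Months 3 and 6.* Not defined as a safety variable. The 10-point cut is one of the thresholds from 1 to 20 in SAP 5.2.1.1, which plans time-to-event tests and hazard ratios as responder analyses. The by-visit responder analysis at Months 3 and 6 (SAP 4.1.4) uses 7 points.

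**Step 2. Exposure-response for safety.** Protocol 9.9 commits to it and SAP 1.1 repeats the objective. SAP 5.5 covers only troughs over time, and SAP 5.6 only plasma Aβ. SAP 1.9 lists one change from the protocol, dropping the Bazett correction. The objective therefore stands without a method in the SAP, and no change is declared.

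**Step 3. Precision of a risk difference.** Inputs: about 400 per arm with A-study and B-study combined (Protocol 3.0), and an assumed common event rate p, since the documents give none. The half-width is 1.96 × √(2p(1 − p)/400).
- p = 5%: 1.96 × √(0.095/400) = 0.030, or 3.0 points
- p = 10%: 1.96 × √(0.18/400) = 0.042, or 4.2 points
- p = 20%: 1.96 × √(0.32/400) = 0.055, or 5.5 points

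For the ADAS-cog item the denominator is subjects assessed at that visit, so its interval will be somewhat wider.

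**Step 4. How close 5 mg/day comes to 47 ng/mL.** Protocol Table 2 gives a mean maximum trough of 16.22 (95% CI 14.59 to 17.85, n = 131) in the 5 mg group. Implied SD: (17.85 − 14.59)/(2 × 1.96) × √131 ≈ 9.5.
- Normal distribution: (47 − 16.22)/9.5 = 3.24 SD, a tail of about 0.0006, so fewer than 1 of 400.
- Lognormal with the same mean and SD: log-SD = √ln(1 + (9.5/16.22)²) ≈ 0.54 and log-mean ≈ 2.64, so z = (3.85 − 2.64)/0.54 ≈ 2.2, a tail of about 0.013, or about 5 of 400.

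This assumes the Phase 2 distribution carries over, with troughs in ng/mL as in the surrounding text.

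**The case against.** The strongest answer is that the signal belongs to a dose not given in this trial. The protocol says it was not noted at 5 mg/day, and Step 4 suggests that few if any subjects would pass 47 ng/mL. This stands. It lowers the priority of the point, and a by-trough display may have little to show in the upper range. It does not remove the case for checking a concentration-related signal at the concentrations actually reached.

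The events are also not lost. Falls and confusion appear by arm in the TEAE tables. Ten-point worsening has a hazard ratio, and Kaplan-Meier curves are planned for time-to-event variables (SAP 5.2.2). Mean ADAS-cog change is estimated at Months 3 and 6, and SAP 1.7 has the IDMC review ADAS-cog for safety. All of this is correct. None of it states a proportion with a 10-point decline at Month 3 and at Month 6, by arm with an interval, as a safety result.

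SAP 5 makes safety evaluation descriptive throughout. That is a legitimate choice, and a descriptive risk difference with a CI fits within it.

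Four stronger readings are tempting and are not supported:
- A reader might infer that confusion is excluded from the special-interest events. The psychiatric SOC may contain it.
- A reader might infer that nothing outside psychiatric terms can be examined. The SMQ clause allows it, although it names no query and depends on what emerges, whereas this signal was known beforehand.
- A reader might infer that the targeted comparison can show only benefit. A comparison of proportions can go either way.
- A reader might infer that nothing connects safety to concentration. Protocol 9.9 does; the SAP does not carry it through.

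**Conclusion.** The point holds as a gap in pre-specified safety focus and early by-visit estimation, not in data collection or reporting. The named special-interest groups were chosen for expected benefit. Falls are not named, confusion is not isolated, and early ADAS-cog decline of 10 or more points has no safety variable. The exposure-response objective for safety has no method in the SAP.

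The size is modest. No primary or secondary efficacy conclusion depends on it, and nothing in the documents predicts the signal at 5 mg/day. The gain is an explicit bound on any excess, to within about 3.0 to 5.5 points either way. That rests on assumed event rates of 5% to 20%, about 400 per arm, and the normal approximation. It describes achievable precision, not an expected harm.

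**What to change.** 1. In SAP 4.5 and 5.4.1, name falls and a pre-specified confusion term grouping as events of special interest, with the term lists fixed before unblinding.
2. Add as a safety variable the proportion of subjects with an ADAS-cog increase from baseline of 10 or more points, at Month 3 and at Month 6 separately.
3. Report each item as number, percent and descriptive risk difference with 95% CI by arm, A-study and B-study combined.
4. In SAP 5.5, add a descriptive display of these events by trough concentration among subjects on azeliragon, to deliver the exposure-response objective in SAP 1.1 and Protocol 9.9.

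The cost is a few extra descriptive tables. Adverse events and ADAS-cog at Months 3 and 6 are already collected, and trough samples are scheduled at Months 3, 6, 12 and 18. No alpha is used, and the existing psychiatric and anxiety groupings can stay.

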## 5 Statistical Methodology

General statistical methods will be applied as appropriate for out-patient clinical studies. Safety evaluations will rely on descriptive statistics. Randomization groups will be examined for homogeneity between treatment groups.

Continuous variables will be summarized using mean, median, standard deviation, minimum, maximum, and number of subjects available for analysis. Categorical variables will be summarized using frequency, proportion, and number of subjects available for analysis.

The primary analysis is completely specified in the protocol, and that analysis is the intended analysis to be advanced as primary. Additionally, supportive analyses, sensitivity analyses, and secondary analyses will be done with respect to the primary endpoint.

SAS version 9.3 or later will be used.

### 5.1 Pooling of Investigator Sites

Blind data review (recommended by ICH E9) has revealed many sites with few subjects randomized. Understanding the influence of site effects on analysis conclusions is essential. Analysis by site is recommended in ICH E9 for key variables of analysis. Site pools are defined as follows:

- Sites with 12 or more subjects randomized will stand alone
- Sites with exactly 11 subjects randomized will be pooled together for Pool 11
- Sites with exactly 10 subjects randomized will be pooled together for Pool 10
- Sites with exactly 9 subjects randomized will be pooled together for Pool 9
- Sites with exactly 8 subjects randomized will be pooled together for Pool 8
- Sites with exactly 7 subjects randomized will be pooled together for Pool 7
- Sites with exactly 6 subjects randomized will be pooled together for Pool 6
- Sites with exactly 5 subjects randomized will be pooled together for Pool 5
- Sites with exactly 4 subjects randomized will be pooled together for Pool 4
- Sites with exactly 3 subjects randomized will be pooled together for Pool 3
- Sites with exactly 2 subjects randomized will be pooled together for Pool 2
- Sites with a single subject randomized will be pooled together for Pool 1.

Site or site pool will be included in analysis and displays using site or site pool as defined above.

Forest plots will be generated by site to the extent feasible to describe key results by site.

### 5.2 Statistical Methodology for Efficacy Analysis

Efficacy evaluations will include the co-primary endpoints (ADAS-cog and CDR-sb), key secondary endpoint, secondary endpoints and other efficacy variables.

The primary analysis of efficacy endpoints will be done on the FAS with supportive and sensitivity analyses done to examine robustness against analysis assumptions and handling of missing data.

Statistical analysis will be done on the A-study and the B-study, independently, for the co-primary variables: change from baseline in ADAS-cog and change from baseline in CDR-sb. The A-study includes the first approximately 400 patients randomized, and the B-study includes the remaining approximately 400 patients randomized. For all other secondary variables and subgroup analyses, the study as a whole (A-study and B-study combined) will be used for inferential purposes. It is noted that randomization supports independent analysis of A-study and B-study.

The primary analysis will be done for the A-study and the B-study separately, and each will use  $\alpha = 0.049$ , which includes an adjustment of 0.001 for interim analyses performed by the Independent Data Monitoring Committee (IDMC), thereby preserving the overall study-wise  $\alpha = 0.05$ .

This study is randomized using site randomization; the study randomization also includes a randomization stratum for severity of AD using a cut-point of 19 on the ADAS-cog at the time of randomization (screening values are used, due to the expectation that a confirming evaluation would be done). Efficacy analyses will be done including randomization stratum as a main effect.

### **5.2.1 Statistical Methodology for Primary Efficacy Analysis**

The primary analysis will be done on change from baseline in ADAS-cog and on change from baseline in CDR-sb.

The primary analysis will use the ITT methodology and a main-effects (for covariates) mixed-models for repeated measures (MMRM) methodology. The MMRM will utilize an unstructured covariance where the number of parameters is  $t(t+1)/2$  where  $t$  is the dimension of the covariance matrix, using PROC MIXED in SAS. In the unlikely event of lack of convergence, Toeplitz structure will be employed where the number of parameters is  $t$  where  $t$  is the dimension of the covariance matrix. Time is considered as a class variable. Analysis will include treatment, time, treatment-by-time interaction, Baseline as covariate, and baseline stratum as a covariate, and subject as a random effect (acknowledging that subject is a source of random variation). This method provides the primary treatment comparison at Month 18. Supportive modeling will also include MMRM main-effects model with treatment, time, and subject.

The primary analysis will also be done on randomization stratification subgroups defined by (1) baseline ADAS-cog 19 or less and (2) baseline ADAS-cog more than 19.

Multiple imputations (MI) will be used as an alternative for coping with missing data as supportive analyses with 100 invocations (acknowledging that more invocations are needed with more missing data). Monte Carlo methods are planned.

The MI analysis assuming Missing at Random (MAR) will be done as follows:

- First, for patients with intermittent missing values, before performing the MI, a monotone missingness pattern will be created. Intermittent missing values will be imputed using the Markov Chain Monte Carlo (MCMC) methodology which assumes a multivariate normal distribution over all variables included in the imputation model. The imputation model will be performed by treatment group and will include age, sex, ApoE status, education level, body weight (or BMI), baseline stratum, baseline and observed values at Months 3, 6, 9, 12, 15 and 18. Months 9 and 12 are not included in the model for endpoints which were not scheduled to be assessed at those visits. The MI procedure in SAS will be used for this purpose and this first MI step is planned to be repeated 100 times, creating several different datasets with a monotone missing data structure. A unique seed value will be used in the MI procedure and documented to allow for replication. The imputation is based on the missing at random (MAR) assumption, i.e. the missing data are assumed to follow the same model as the other patients in their respective treatment arm.
- After this, the remaining missing data will be imputed using a method for monotone missingness, also based on the MAR assumption. Thus, for each of the 100 created datasets with a monotone missing data pattern, the MI procedure in SAS will be used to impute missing values based on a sequential procedure reflecting the monotone missing data pattern. A seed value of 446786 will be used for this second invocation of the MI procedure. Patients with the first missing value occurring at Month 3 will have their missing Month 3 value replaced by an imputed value from a regression model by treatment group with age, sex, ApoE status, education level, BMI, baseline stratum, and baseline as potentially predictive variables.
- In the next step, patients with the first missing value occurring at Month 6 will have their missing Month 6 value replaced by an imputed value from a regression model with Month 3 data, in addition to the variables listed above.
- The same procedure will be repeated for all other visits.
- The imputed datasets generated with the approach described above do contain only non-missing values and are used as input in the model for the supportive analysis of the primary endpoint. MMRM models similar to what are described above will thus be run on each of the generated imputed datasets and the difference between the treatment groups at Month 18 will be estimated. The MMRM model will be similar to the primary analysis. Finally, the MIANALYZE procedure in SAS will be applied to combine the results from these several datasets to derive an overall estimate of the treatment difference at Month 18. In addition to the estimates, corresponding 95% confidence intervals and p-values will be calculated.

Another MI analysis will be performed with the assumption that the data in the active treatment group are missing not at random (MNAR). A tipping point-based assumption will be used, i.e. the trajectories of the patients in the active treatment group after withdrawal are assumed to be worse by an amount of delta. After the MI using the MAR assumption, as defined above has been done, the amount of delta will be added to each imputed value in the active treatment group. Successively harsher deltas will be imposed on the imputed values in the active group, starting with an ADAS-cog increment (worsening) of 0.25 points or a CDR-sb increment

(worsening) of 0.1 points. The delta is further increased in the steps of 0.25 points (e.g., 0.50, 0.75) for ADAS-cog or in the steps of 0.1 points (e.g., 0.2, 0.3) for CDR-sb until the statistical significance is lost, i.e., until the p-value becomes more than 0.049. For the placebo group, the MI using MAR assumption will be used.

Further MI analysis assuming MNAR will be done using the Copy Reference approach. Placebo-group based assumption will be used, i.e. the trajectories of the patients are assumed to follow the placebo group after the discontinuation. Methods similar to those described above will be used to generate monotone missing data. After this, the missing data will be imputed sequentially for each visit (e.g., Month 3, Month 6). Only the data from the placebo group will be used for the imputation.

For the ANCOVA models, data from baseline and Month 18 will be used. Analysis will include treatment, baseline stratum as fixed factors and Baseline as covariate. For the LOCF analysis, the last available measurement will be used to impute the Month 18 data in case of missing data.

Rank analogues (e.g., Wilcoxon analysis, rank ANCOVA, and van Elteren analysis when strata are a part of the approach) will be used for additional supportive analyses. An observed-cases analysis will be done by visit.

An essential component of the thorough analysis includes an assessment of the impact of missing data on study conclusions. As a part of assessing this impact, sensitivity analysis will include an endpoint analysis (reduction to last-observation-carried-forward, justified in this study based on the monotonic progression of the natural course of AD and assuming no more dropouts in the group treated with azeliragon plus SoC than in the group treated with placebo plus SoC), a completers analysis (observed cases at Month 18), and observed cases by assessment time.

Interaction terms will be examined in the supportive analyses. The primary model will not include interaction terms with covariates. In the event of a significant interaction term, the impact on analysis conclusion will be examined. A key sensitivity analysis will use the ITT methodology and a main-effects model for ANCOVA adjusting for baseline ADAS-cog (CDR-sb) using last-observation-carried-forward (LOCF) methods for missing data, justified based on known profiles of ADAS-cog (CDR-sb) in AD patients, which is conservative under the assumption that there are not more dropouts in the active-treated group than the placebo group. Rank ANCOVA will be done as a supportive analysis.

Additional unplanned sensitivity analyses may be performed.

Descriptive summaries will be produced of the observed values and change from Baseline in co-primary variables by treatment group at each individual time point and at endpoint (final on-treatment assessment for each subject).

For statistical analyses, 95% confidence intervals will be produced for the least-squares means (LSM) in each treatment group, as well as the LSM differences as compared to placebo plus SoC. For MMRM and ANCOVA, two-sided p-values will be displayed for the comparison against placebo plus SoC.

Because there are limited numbers of subjects per center, there will be inadequate power to explore the impact of the center effect on study conclusion. Descriptive statistics by center will be presented.

The differences in the least squares means between Azeliragon and placebo, p-values, standard errors of the differences, and corresponding 95% confidence intervals for the differences will be presented. In addition, the least-squares means and corresponding 95% confidence intervals will be presented for each treatment group.

